Study Protocol and Statistical Analysis Plan

B. SIGNIFICANCE:

B.1 Recurrent urinary tract infections in older women are common, poorly understood, and complicated by confounding symptom overlap.

Urinary tract infection (UTI) is the most common bacterial infection, accounting for more than 8 million office visits and 1 million emergency department visits each year in the United States.² Importantly, ~80% of visits for UTI are in women,³² and the highest rates of UTI recurrence occur in older women³³ who also have more variation and antibiotic resistance in the uropathogens that cause UTIs.^{5,34} It is clear that menopause is a predominant risk factor for rUTI and that the pathophysiology of a single, sporadic UTI in premenopausal women is very different than that of rUTI in older women.^{8,35} In older women with patient reported UTI, given the symptom overlap between overactive bladder and genitourinary syndrome of menopause, the diagnosis of acute UTI should be made using a combination of symptom assessment and urine diagnostic studies.^{14,36}

Although dysuria seems to be the most discriminating symptom for a culture-positive UTI,³⁷ we are still unable to reliably predict other factors that correlate with culture positivity and who will require antibiotics to clear a symptomatic UTI.³⁸ Prospective investigations are crucial to improve our ability to predict those that may have symptom resolution without antibiotic therapy, but also those that can be safely managed with a urine culture-directed antibiotic strategy.

B.2. Preliminary observational data suggests that a urine culture-directed antibiotic strategy for patient reported UTI in older women is safe, but randomized controlled trials are needed to substantiate broad adoption of such a strategy.

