Non-antibiotic treatment and placebo as initial management of UTI symptoms have been evaluated in several randomized controlled trials (RCTs) that enroll a mostly premenopausal population.^{16,39-43} An initial non-antibiotic strategy leads to a decrease in overall antibiotic use given either resolution of symptoms,¹⁸ or lack of bacteriuria.¹⁹ The results of these trials suggest that initial non-antibiotic management can be reasonable, but it may not be the method of choice for every woman with uncomplicated UTI. The literature on non-antibiotic treatment as initial management for UTI symptoms in older women is limited as the majority of studies did not enroll participants over the age of 65-70 and had a participant mean age of 30-40 years^{16,39-43} even though older women are an especially vulnerable population for drug interactions due to age-related physiologic changes and higher concomitant medication use.⁴⁴

Preliminary data: Recently, we performed a prospective cohort study on 152 women who were seeking care for UTI symptoms with mean age 66.4 (SD 14.9) of which 52.0% had a history of recurrent UTI. Women completed the UTI symptom assessment (UTISA) questionnaire⁴⁵ before they submitted a culture and then were either placed on empiric antibiotics or managed expectantly based on provider and/or patient preference. After urine cultures were resulted, participants completed another UTISA questionnaire and the global rating of change (GRC). Our primary outcome was “symptom improvement” defined as reporting symptoms of “better” on the GRC questionnaire.

Overall, 122 (80.3%) were managed expectantly, 30 (19.7%) were managed with empiric antibiotics.

The proportion of positive UCx in those treated empirically (53.3%) was similar to those managed expectantly (59%) (Table 1) which

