Importantly, the use of screening tests to assess whether prospective participants are appropriate candidates for inclusion in studies is an appropriate pre-entry activity. Per research guidelines, an investigator may discuss availability of studies and the possibility of entry into a study with a prospective participant without first obtaining consent when no clinical procedures performed solely for the purpose of determining eligibility for research are planned.⁶⁴ Importantly, electronic approaches are becoming more widely used to obtain informed consent for research participation. Electronic consent (e-consent) provides an accessible and versatile approach to the consenting process, which can be enhanced with audio-visual and interactive features to improve participant engagement and comprehension of study procedures. E-consent may facilitate remotely conducted research by offering a feasible and robust alternative to face-to-face consenting approaches, however we will offer paper-based options, based on participant preference.⁶⁵⁻⁶⁷

D.1.3.2 Enrollment and Randomization (Day 0).

- Upon development of symptoms (Figure 2), interested women will be scheduled for a baseline study visit (either in-person or virtual based on participant preference).

Table 2: Detailed Inclusion and Exclusion Criteria

Inclusion Criteria

- Female biologic Sex
- Age ≥65 years old
- History of recurrent UTI per patient report of greater than 2 UTIs in the last 6 months or 3 UTIs in the last year
- Patient reported UTI defined as:
 - Dysuria, increased urinary urgency/frequency and/or suprapubic pain

Exclusion Criteria

- Male biologic sex
- Age <65 years old
- History of augmentation cystoplasty or cystectomy
- Currently performing clean intermittent self-catheterization
- Current indwelling foley catheter
- Urinary tract instrumentation (i.e., cystourethroscopy, foley catheter placement) in the last 30 days
- Undergoing treatment for malignancy
- History of either confirmed or patient reported pyelonephritis and/or urosepsis
- Cirrhosis and/or end stage liver disease
- Chronic kidney disease with most recent estimated glomerular filtration rate <50 ml/min
- Dementia and/or currently reside in skilled nursing facility
- Current high-dose chronic steroids (>20mg/day of prednisone)
- Previous solid organ transplant
- Provider concern for pyelonephritis and/or sepsis (i.e., fevers)
- Unwilling or unable to comply with study procedures

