- This visit will first take place with a research coordinator where the participant will be allowed to ask any final questions about their consent which will then be signed either on paper or electronically.
- Final eligibility will be determined by a licensed medical provider on the research team by ensuring the participant is not experiencing any symptoms of pyelonephritis and/or sepsis.
- Consented study participants will then complete baseline questionnaires including the Urinary Tract Infection Symptom Assessment (UTISA)⁶⁸ and the pelvic floor distress inventory short form (PFDI-20).⁶⁹
- Participants will submit a urine specimen for urine culture and urinalysis either in-person at one of our Women's Center for Bladder and Pelvic Health faculty practices or a local laboratory

Randomization: Participants will be randomized by the study team to either the “Culture-directed Antibiotic Treatment” or “Empiric (Immediate) Antibiotic Treatment” Group in a 1:1 allocation scheme, with randomization using permuted blocks of 4 or 6.

D.1.3.3 Antibiotic Treatment Strategy. All participants will be allowed to use acetaminophen, non-steriodals, and/or phenazopyridine.

Culture-directed Antibiotic Treatment: Participants will be directed to refrain from taking antibiotics until results of urine culture are reported, which is expected within 48-72h.

Empiric Antibiotic Treatment Participants will be prescribed empiric antibiotics in accordance with our stepwise protocol below.

Antibiotic Protocol. For participants in the empiric Rx arm, we will choose an antibiotic with consideration of patient reported allergies, current medications and current IDSA guidelines.⁷⁰ If there is a contraindication to the first antibiotic on the list they will progress to the next option until a suitable selection is achieved.

Antibiotic Protocol:

1. Nitrofurantoin 100 mg PO BID x 5 days
2. Trimethoprim/Sulfamethoxazole 875/125 mg PO BID x 5 days
3. Fosfomycin 3 g once
4. Cephalexin 500 QID x 5 days
5. Ciprofloxacin 500 mg PO BID x 5 days

D.1.3.4 Antibiotic management after urine culture results. All participants will be called with the results of their culture. Participants who register for *MyUPMC*, a no-cost, proprietary secure email service, will also receive the urine culture result by email. Cultures with result of “mixed flora” will be considered contaminated and be managed as negative.⁷¹

Culture-directed Antibiotic Treatment.

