For a larger trial, electronic surveys may significantly reduce research coordinator burden. To evaluate feasibility of this approach we will administer electronic surveys through Research Electronic Data Capture (REDCap) software.⁷² Surveys are sent via email and can be accessed through either a laptop, desktop or smart phone. Participants will also be called at day 2-3 (after urine culture results) and then weekly to assess issues with electronic materials. We will evaluate proportion of those with electronic success and investigate demographic variables that may be associated with inability to utilize electronic materials. To assess patient adherence to study procedures, defined as completion of all follow-up questionnaires, we will describe the percentage of enrollees who completed 100% of study procedures, 80% to 100% of study procedures and 50% to 80% of study procedure. A priori, we believe that compliance with 70% of study procedures will demonstrate satisfactory patient adherence to protocol. If the underlying adherence rate is 70%, a sample size of 70 provides a 10.1% MoE.

Exploratory Aim: To explore the safety of a culture-directed UTI treatment strategy and preliminary secondary outcomes of assigned treatments.

Safety Aims⁶²

1. Adverse events per group (most likely antibiotic side effects (i.e., gastrointestinal distress, antibiotic related diarrhea, rash) between groups.
2. Serious adverse events per group (defined in line with FDA reporting guidelines as a medical event that does one or more of the following: results in death, is life - threatening, requires inpatient hospitalization or prolongation of existing hospitalization, results in persistent or significant disability/incapacity, or is a congenital anomaly/birth defect.⁷⁷

Analysis. We anticipate that adverse events will be reported relatively infrequent.⁷⁸ All outcomes will be described using numbers and proportions of patients. Proportions between groups will be compared with either chi-square or Fischer's exact testing.

Secondary exploratory aims.

Proportion of those with clinical cure (as 2 or less points (slight, very slight, or no problems) on all five components of the UTISA (ref) at day 14 (***future trial primary outcome***)

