Analysis. All outcomes will be described using numbers and proportions of patients or means with confidence intervals. Proportions between groups will be compared with either chi-square or Fischer's exact testing and means will be compared with student's t-testing. Exploratory logistic regression modeling will be utilized to investigate the odds of both initial treatment failure and/or recurrent of UTI symptoms between groups and based on baseline characteristics

Power analysis:^{76,79} As above, we propose a future trial with a primary outcome to be symptom resolution at day 14 defined as 2 or less points (slight, very slight, or no problems) on all five components of the UTI symptom assessment (UTISA).^{43,78} The literature suggests 58-80% of women receiving empiric antibiotics for patient reported UTI will achieve clinical cure by day 3-7 after treatment initiation.^{43,78} Given that only women

with a positive urine culture will be given culture-directed antibiotics, and women in the empiric arm may have to have their antibiotics changed or stopped at the time of culture result, we anticipate a higher proportion of those in the culture-directed arm to have symptom resolution at day 7. Assuming 70% symptom resolution in the empiric arm, a future trial of 262 participants, with 131 per arm, would have 80% power to detect a 15-percentage point difference between groups with a 2-sided alpha of 0.05, while a sample size of 300 would be required assuming 65% resolution. Therefore, we believe that successfully recruiting a total of 70 participants at a rate of 6-7 participants/month will confirm the feasibility of future trial completion in <4 years (equivalent to other trials of antibiotic regimens for symptomatic UTI).^{17,78}

Statistical methods

Primary Outcomes	Statistical analysis
Feasibility: 
 - Number of subjects that were screened for participation - Number and proportion of subjects screened who met inclusion/exclusion criteria - Number and proportion of subjects who either declined participation or were ineligible (including reasons for ineligibility) - Number and proportion of eligible subjects that were enrolled in the study - Number and proportion of subjects enrolled who completed the study - Monthly enrollment rate 	Descriptive analysis = counts and proportions or means with standard deviation

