Adherence: 
 - Number of those that completed all study procedures - Number of subjects that took alternative agents taken by subjects for management of symptoms - Number of subjects in the culture-directed arm that acquired off-protocol antibiotics for their symptoms - Number of subjects able to complete electronic surveys 	Descriptive analysis = counts and proportions
Secondary Outcome	
Proposed primary outcome for future trial (Clinical Success at 14 days UTISA 1-3,5<=1)	Descriptive analysis = counts and proportions Comparative = Chi-square

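### Day-14 cure is an absolute UTISA score with no reference to Day 0, so it may count some women as cured before treatment and others as not cured after full recovery

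*Combined protocol and SAP*

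**What the plan says.** - **Entry (Table 2).** Patient-reported UTI is "Dysuria, increased urinary urgency/frequency and/or suprapubic pain". Any one symptom is enough. Only urgency/frequency has to have increased; dysuria and suprapubic pain qualify by being present. No minimum severity or UTISA score is set.
- **Baseline (D.1.3.2).** Before randomisation, "Consented study participants will then complete baseline questionnaires including the Urinary Tract Infection Symptom Assessment (UTISA") and the PFDI-20.
- **Cure, first statement (D.1.7, Secondary exploratory aims).** At day 14: "Proportion of those with clinical cure (as 2 or less points (slight, very slight, or no problems) on all five components of the UTISA". The Power analysis repeats this rule as the primary outcome of the future trial.
- **Cure, second statement (Statistical methods table).** "Proposed primary outcome for future trial (Clinical Success at 14 days UTISA 1-3,5<=1", which uses four items and a lower cut-off.
- **Chronic symptoms (B.1).** Diagnosis in older women needs both symptoms and urine tests, "given the symptom overlap between overactive bladder and genitourinary syndrome of menopause". Table 2 does not exclude overactive bladder.
- **Use of baseline in analysis (D.1.7).** "Exploratory logistic regression modeling will be utilized to investigate the odds of both initial treatment failure and/or recurrent of UTI symptoms between groups", and by baseline characteristics. The outcomes named are failure and recurrence. Cure itself is not redefined.
- **Change measure.** In the preliminary cohort (B.2), "participants completed another UTISA questionnaire and the global rating of change (GRC"). The follow-up list in D.1.6 has no such item.

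**The concern.** Entry and outcome use different yardsticks. A woman enters because she reports a symptom of any severity or, for urgency/frequency, because it has risen above her usual level. She is judged at day 14 against a fixed ceiling that takes no account of where she started or of her usual state. Two kinds of misclassification become possible:

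1. A woman whose scored items are all at or below the cut-off at Day 0 already meets the rule before any strategy is applied.
2. A woman with chronic urgency/frequency above the cut-off may clear her infection, return to her usual state and be counted as not cured.

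The second is plausible on the plan's own account, given B.1 and recruitment partly through a pelvic-floor practice (D.1.2).

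In this pilot the outcome is exploratory. It matters because the plan names it as the future trial's primary outcome, and because the pilot exists to inform that trial's methods. A pilot cure rate that mixes response to the strategy with entry severity and long-standing bladder symptoms is a weak basis for the next sample size.

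**Working it through.** **Step 1: the two rules applied to the two kinds of patient**

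| | At most 2 on all five components (D.1.7) | At most 1 on items 1-3 and 5 (methods table) |
|---|---|---|
| Refers to Day 0? | No | No |
| Worst Day 0 symptom is slight (2), on a scored item | Already meets cure | Does not meet cure |
| All scored items very slight or absent at Day 0 | Already meets cure | Already meets cure |
| Back to a usual score above the cut-off on a scored item | Not cured | Not cured |

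Reading slight as 2 follows the order of the labels in D.1.7. The lower cut-off lets fewer mild scores on the scored items count as cure at Day 0, but it puts more chronic symptoms above the line.

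**Step 2: the plan's own sample size**

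Inputs from the Power analysis: 70% in the empiric arm, a 15-point difference (so 85%), two-sided alpha 0.05, 80% power, 131 per arm.

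- Two-sided Fisher exact test, exact power: 80.1% at 131 per arm and 79.7% at 130. The stated 262 reproduces.
- For 65% versus 80%: 80.3% at 150 per arm. The stated 300 reproduces.

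The arithmetic is sound. The point concerns the endpoint.

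**Step 3: sensitivity to the two groups**

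The documents give no UTISA distribution, so these shares are assumptions:

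- s = share meeting cure at Day 0 and still meeting it at day 14 in either arm;
- c = share above the cut-off on some item at day 14 in either arm;
- 70% versus 85% applies to the remaining 1 - s - c.

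Arm rates are p1 = s + (1 - s - c) x 0.70 and p2 = s + (1 - s - c) x 0.85. The difference is d = 15 x (1 - s - c) points.

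For comparison across rows, power uses the pooled normal formula at n = 131 per arm (p̄ is the mean of p1 and p2):

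z = [d√n - 1.96√(2p̄(1 - p̄))] / √(p1(1 - p1) + p2(1 - p2))

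Total N for 80% power uses the same approximation with continuity correction. With no dilution these give 83% and 268, so later rows should be compared with those figures and not with 80% and 262.

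| s | c | p1 | p2 | Difference (points) | Power at 131 per arm | Total N |
|---|---|---|---|---|---|---|
| 0 | 0 | 70.0% | 85.0% | 15.0 | 83% | 268 |
| 10% | 0 | 73.0% | 86.5% | 13.5 | 78% | 306 |
| 0 | 10% | 63.0% | 76.5% | 13.5 | 66% | 392 |
| 5% | 5% | 68.0% | 81.5% | 13.5 | 71% | 352 |
| 10% | 10% | 66.0% | 78.0% | 12.0 | 58% | 470 |
| 20% | 20% | 62.0% | 71.0% | 9.0 | 34% | 906 |

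Example, s = c = 5%: p1 = 0.05 + 0.90 x 0.70 = 0.68; p2 = 0.05 + 0.90 x 0.85 = 0.815; d = 0.135.

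**Step 4: ceiling**

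Under the same assumption, cure cannot exceed 1 - c in either arm. The planned 85% is out of reach once c is above 15%.

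For equal shares, c costs more power than s, because it pulls the rates towards 50%, where the variance is larger.

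**The case against.** The strongest reply is that this is a secondary, exploratory outcome in a feasibility pilot of 70 women. The primary outcome is recruitment and adherence, and broad entry is a deliberate pragmatic choice (D.1.2). That stands, and it limits the weight of the point. It does not remove it, because the plan carries this same outcome forward as the future primary.

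The reply also rightly blocks four stronger readings that a reader might infer:

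- *Some women are cured at Day 0 and others can never be cured.* The wording allows both, but the documents show neither. No baseline scores are given, and a chronic score may fall.
- *All women enter on an increase over their usual symptoms.* Table 2 says so only for urgency/frequency.
- *The slight-symptom example holds under either cut-off.* It fails for scored items under the methods-table rule.
- *The strategy cannot affect these women's results.* A mild entrant can worsen by day 14, and staying well is then a real outcome. This is a reason to keep all randomised women in one version of the analysis.

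The magnitudes can be challenged too. The plan states 70% and 15 points for whole arms, and those figures may already include both kinds of patient. Nothing in the documents settles this. One of the two references behind the 58-80% range is also listed in B.2 among trials of mostly premenopausal women, so it cannot be assumed that chronic symptoms at age 65 and over are reflected in it. For mild entrants alone, the effect at s = 10% is modest: 83% to 78%.

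Finally, the Day 0 UTISA and PFDI-20 are collected and an exploratory regression on baseline characteristics is planned. Neither changes who is counted as cured.

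**Conclusion.** The point holds as a weakness in the endpoint definition. Both cure rules are absolute, entry has no severity floor, and the Day 0 UTISA plays no part in the outcome. The rule as written may therefore credit a woman who met it before treatment, and may fail a woman who is back to her usual state.

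A reader might go on to infer a biased comparison. The documents do not support that. Allocation is 1:1 at random, so both groups should balance on average. Chance imbalance with about 35 women per arm is possible, as for any covariate. The expected harm is dilution and a pilot cure rate that is hard to interpret for planning.

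Its size is unknown. With assumed shares of 5% to 20% in each group, the 15-point difference becomes 13.5 to 9.0 points, and total N rises from 268 to between 352 and 906. These figures rest on three assumptions: the shares themselves, fixed status by day 14 in both groups, and 70% versus 85% in the rest. They show why the shares are worth measuring and are not a forecast. The change is a cheap improvement that should be made; the pilot's feasibility aims do not depend on it.

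**What to change.** 1. Reconcile the two cure rules, so that one cut-off and one set of items applies throughout.
2. Report by arm how many women already met the chosen rule at Day 0.
3. Keep the absolute definition in all randomised women, so that a mild entrant who worsens still counts as a failure.
4. Pre-specify an added analysis of day-14 cure among women with at least one scored component above the cut-off at Day 0. The Day 0 UTISA is completed before randomisation, so this subgroup comparison remains a randomised one.
5. Optionally, ask each woman at Day 0 to score the same items for her usual state, and report a sensitivity version that counts an item as resolved if it is at or below the cut-off or back to the usual score. This should not become the main definition: it relies on recall during an acute episode, and the documents offer nothing on its validity.

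Items 1 to 4 need only changes to the analysis text, because the data are already collected. Item 5 adds up to five questions to one form. The costs are a smaller denominator in the added analysis and recall error in the optional score.

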- Those with a negative urine culture will not be prescribed antibiotics and will be followed per protocol.
- Those with a positive urine culture who *report persistent UTI symptoms* will be given antibiotics following the priority list above with consideration to reported antimicrobial sensitivities.
- Those with a positive urine culture who *report resolution of UTI symptoms* will not be given antibiotic

Empiric Antibiotic Treatment.

- Those with a negative urine culture will be told to stop antibiotics
- Those with a positive urine culture sensitive to the empiric antibiotic will be instructed to complete the full course of their antibiotics
- Those with a positive culture resistant to empiric antibiotic will be given an alternative antibiotic per antibiotic protocol and will be followed per protocol. If there are no oral antibiotic options with patient-specific and antimicrobial sensitivities, we will engage local infectious disease physicians for management as per standard clinical protocols.

[figure not shown]
D.1.6. Study follow-up assessments.

All participants will be followed with electronic surveys via Research Electronic Data Capture (REDCap) software, which is a browser-based, metadata-directed EDC software and workflow methodology for designing

clinical and translational research databases,⁷² on day 2-3 (after result of urine culture). To avoid limiting enrollment to only those with access to technology, our research coordinator can also call and administer the questionnaire by phone to ensure ability to access and complete electronic materials. Follow-up assessments will be completed weekly for a total of 4 weeks. These will include UTISA questionnaire,⁶⁸ antibiotic associated side effects, use of other symptom mitigating remedies, and adherence to assigned study arm.

Participants will be provided with a clinical line to call 24/7 with report of worsening symptoms which will be discussed with the PI, [name] for determination of antibiotic prescription and if participants report fevers or chills this will prompt an in-person evaluation in clinic during business hours or the emergency department after hours. If participants call to report new symptoms during the study course, a repeat urine culture will be obtained.⁷³ Given that these episodes could be considered either a recurrent or incompletely treated infection we plan to manage these per clinical care and not based on the participants initial study arm.

Figure 2: Study Flow Diagram

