
Pelvic floor distress inventory, PFDI-20; Urinary Tract Infection Symptom Assessment, UTISA
 * Adverse events will include either antibiotic related side effects, signs/symptoms of pyelonephritis and/or urosepsis or other serious adverse events

D.1.7. Data analysis.

Specific aim 1A) To evaluate the feasibility of recruiting eligible participants into a randomized trial of a culture-directed versus empiric antibiotic strategy for patient-reported UTI symptoms in older women.
 All outcomes for the feasibility assessment will be descriptive using numbers and proportions of patients and 95% CIs. We will report the number of patients assessed for eligibility along with the numbers excluded based on not meeting inclusion criteria, participation declined, and other reasons.⁷⁴ We will document number and proportion of enrolled participants who were randomized along with the number/proportion who received their

allocated assignment. We will document those lost-to follow-up including potential reasons. These data will provide information on the feasibility of recruiting patients into a future, large randomized, placebo controlled clinical trial. We believe that successfully recruiting 10% of eligible patients (e.g., 6-7 patients per month) will confirm the capacity to recruit for a future trial.

Power calculation:^{75,76} The primary outcome is feasibility which we will define as the ability to recruit 10% of eligible patients. As this is a pilot study, the sample size of 70 patients was determined based on clinical and logistical resources rather than statistical requirements for hypothesis testing. We anticipate screening approximately 1200 potentially eligible patients (based on known clinical data from our practice and current enrollment of women with recurrent UTI in Pitt+Me®) during the 12 months of recruitment (~100 per month) of which at least 800 will be deemed eligible and have UTI symptoms. (~67 per month) This is based on data from our group on urine cultures sent annually and time between UTI episodes.³⁵ A 95% confidence interval (CI) for the recruitment rate provides a 2.4% margin of error (MoE) assuming the true rate is 10%.

Specific aim 1B) To evaluate participant adherence to study procedures.

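### The exploratory between-arm comparisons leave out the Day 0 UTISA score, giving up a modest, correlation-dependent amount of precision at 35 v 35

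*Combined protocol and SAP*

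**What the plan says.** All references are to the combined protocol and SAP.

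- **Baseline.** D.1.3.2 (Day 0): "Consented study participants will then complete baseline questionnaires including the Urinary Tract Infection Symptom Assessment (UTISA"). This step is listed before the randomisation paragraph, which gives 1:1 allocation in permuted blocks of 4 or 6 and mentions no stratification.
- **Follow-up.** D.1.6 schedules a survey at day 2-3, and then: "Follow-up assessments will be completed weekly for a total of 4 weeks. These will include UTISA questionnaire".
- **Outcome.** The one efficacy outcome listed under the secondary exploratory aims in D.1.7 is binary, at day 14: "Proportion of those with clinical cure (as 2 or less points (slight, very slight, or no problems) on all five components". It is marked as the future trial's primary outcome.
- **Analysis.** The paragraph below it states: "Proportions between groups will be compared with either chi-square or Fischer's exact testing", and "means will be compared with student's t-testing". The Statistical methods table gives, for the day-14 outcome, "Comparative = Chi-square".
- **Regression.** The same paragraph plans an exploratory logistic model for initial treatment failure and/or "recurrent of UTI symptoms between groups and based on baseline characteristics". Failure is not defined and no covariate is listed.
- **Status.** D.1.7, Power calculation: "the sample size of 70 patients was determined based on clinical and logistical resources rather than statistical requirements for hypothesis testing".

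**The concern.** A symptom score taken before allocation is a natural candidate predictor of the same score, or of cure based on it, two weeks later. The trial collects it, but the stated comparisons do not use it. Because no stratification is stated either, neither design nor analysis deals with a chance difference in severity between two small arms. If baseline severity is prognostic, the reported intervals are wider than the collected data require, and a visible imbalance would leave the reader without a prespecified adjusted estimate. The pilot would also end without a planned estimate of how strongly Day 0 UTISA predicts day-14 status, which would be useful when the definitive trial is designed.

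**Working it through.** **Step 1. The plan's own figure.** The pilot has no power statement for day-14 cure; the future-trial size is the nearest figure. Inputs (D.1.7, Power analysis): 70% v 85%, two-sided alpha 0.05, 80% power, stated N 262.

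- Pooled formula: n = [1.960 × √(2 × 0.775 × 0.225) + 0.842 × √(0.21 + 0.1275)]² / 0.15² ≈ 120.5, so 121 per arm, 242 in total.
- With continuity correction: 134 per arm, 268 in total.
- Enumerated power of Fisher's exact test is 80.1% at 131 per arm, and 80.3% at 150 per arm for 65% v 80%.

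Both 262 and 300 are therefore reproduced under Fisher's test. This point exposes no wrong figure.

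**Step 2. Chance imbalance at baseline.** Assume 35 per arm (70 at 1:1) with complete data.

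- SE of the baseline difference = √(2/35) = 0.239 SD.
- P(|difference| > 0.25 SD) = P(|Z| > 0.25/0.239) = 30%; above 0.3 SD, 21%; above 0.5 SD, 3.6%.
- Expected shift in an unadjusted mean difference = rho × imbalance. For 0.25 SD it is 0.075 SD at rho 0.3 and 0.125 SD at rho 0.5. For 0.5 SD it is 0.15 and 0.25 SD.

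**Step 3. Precision for a UTISA mean.** The documents give no correlation rho between Day 0 and follow-up UTISA, so a range is assumed. ANCOVA variance relative to the t-test = (1 - rho²) × (1 + 1/66), where the last factor is the cost of estimating the slope. The t-test's 95% half-width is 0.477 SD.

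| rho (assumed) | Variance ratio | ANCOVA 95% half-width (SD) | Equivalent total N (70 / ratio) |
|---|---|---|---|
| 0 | 1.015 | 0.481 | 69 |
| 0.2 | 0.975 | 0.471 | 72 |
| 0.3 | 0.924 | 0.459 | 76 |
| 0.5 | 0.761 | 0.416 | 92 |
| 0.6 | 0.650 | 0.385 | 108 |

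**Step 4. Precision for day-14 cure.** Take 70% v 85% from the power analysis.

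- Unadjusted half-width = 1.96 × √(0.21/35 + 0.1275/35) = 0.192, about 19 percentage points.
- Expected failures = 35 × 0.30 + 35 × 0.15 = 15.75.
- Simulation (4,000 runs per setting; standard normal baseline; logistic model with arm and baseline; risk difference standardised over all 70 women):

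| OR for cure per SD of baseline (assumed) | Mean correlation of baseline with cure | Variance, adjusted / unadjusted |
|---|---|---|
| 1.00 | 0.00 | 1.02 |
| 0.74 | -0.12 | 1.01 |
| 0.55 | -0.23 | 0.97 |
| 0.37 | -0.34 | 0.89 |

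As a check, the Step 3 formula with the last correlation gives (1 - 0.34²) × 1.015 = 0.90, close to the simulated 0.89. At that setting the half-width falls from 19.2 to 19.2 × √0.888 = 18.1 points.

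**The case against.** The case for leaving the plan alone is substantial, and much of it stands.

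- **The t-test may not be aimed at UTISA.** A reader might infer that UTISA means are a planned comparison. The documents do not say so: the t-test clause is generic and the only named efficacy outcome is binary. UTISA is the likeliest target, since the text schedules no other scored questionnaire at follow-up. That cannot be fully confirmed, because Figure 2 is not shown and its abbreviation note also lists the PFDI-20. The ANCOVA advice is therefore conditional.
- **The tests are not wrong.** A reader might infer that they are biased, or that an imbalance passes in full into the estimate. Neither follows. Randomisation makes the unadjusted tests valid, the imbalance enters multiplied by rho, and its contribution is already part of the unadjusted standard error. Imbalance and precision are one argument, not two.
- **The gain is not free.** It is a slight loss at rho 0. A low rho at day 14 is plausible: every woman enters with symptoms, and the power analysis cites 58-80% cured by day 3-7 on empiric antibiotics.
- **Some adjustment is planned.** The exploratory logistic model might be meant to cover non-cure. As written it cannot be relied on for that, with failure undefined and no covariate named, and the table assigns chi-square alone to day-14 cure.
- **Little hangs on it.** A reader might infer that the pilot's cure difference sets the definitive trial's size. The power analysis uses literature rates and an assumed 15-point difference, and the end of B.3 expects enrolment willingness, initial safety data and qualitative information from the pilot.

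What survives is narrow: a baseline value is collected, the stated comparisons do not use it, and using it costs almost nothing.

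**Conclusion.** The point holds as a minor improvement to an exploratory analysis, not as an error. The stated comparisons are valid but ignore Day 0 UTISA. For a UTISA mean, the change in variance runs from +1.5% (rho 0) through -2.5% (0.2), -8% (0.3) and -24% (0.5) to -35% (0.6). For day-14 cure, the outcome that the plan actually names, it is about +2% to -11%, so the benefit there is small and may be nil. These figures assume 35 analysed per arm, the correlations and odds ratios shown and, for cure, 70% v 85%; none of the correlations or odds ratios comes from the documents. The feasibility primary outcome and the future-trial sizes of 262 and 300 do not change.

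**What to change.** In D.1.7 (Secondary exploratory aims, Analysis) and the Statistical methods table:

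1. State whether UTISA scores will be compared as means. If so, replace the t-test by ANCOVA of the follow-up score on arm and Day 0 UTISA, and report the adjusted difference with its 95% CI.
2. For day-14 cure, add a risk difference with 95% CI, standardised from a logistic model containing arm and Day 0 UTISA only. About 16 expected failures will not support a longer covariate list. Keep the unadjusted chi-square or Fisher's test as supportive.
3. Report the observed correlation of Day 0 UTISA with day-14 UTISA and with day-14 cure, for use in designing the future trial.
4. Define treatment failure and list the covariates for the logistic model already planned.

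The cost is a few sentences of SAP text, a few lines of code and one degree of freedom per model. No new data are needed.
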